#### **2.1.2 Primary endpoints**

The following pharmacokinetic parameters will be determined for BI 425809 and for memantine:

- $AUC_{\tau,ss}$  (area under the concentration-time curve of the analyte in plasma at steady state over a uniform dosing interval  $\tau$ )
- $C_{max,ss}$  (maximum measured concentration of the analyte in plasma at steady state over a uniform dosing interval  $\tau$ )

#### **2.1.3 Secondary endpoint**

Not applicable.

#### 2.2.2.2 Safety and tolerability

Safety and tolerability of BI 425809 will be assessed based on:

- Adverse events (including clinically relevant findings from the physical and neurological examination)
- Safety laboratory tests
- 12-lead ECG (only abnormal findings will be reported as AE)
- Visual tests (only abnormal findings will be reported as AE)
- Vital signs (blood pressure, pulse rate)
- Suicidality assessment (C-SSRS)

### 3. DESCRIPTION OF DESIGN AND TRIAL POPULATION

#### 3.1 OVERALL TRIAL DESIGN AND PLAN

The study will be performed in healthy male and female subjects and is designed non-randomized, single-arm, open-label, three-period, one fixed sequence cross-over to investigate the effects of steady state exposures of memantine on steady state pharmacokinetics of BI 425809 and vice versa.

Considering the well-known safety profiles of the selected dose of BI 425809 and memantine, the unlikelihood of increased drug exposures due to a pharmacokinetic memantine-BI 425809 interaction and the already implemented safety measures (ref [Section 1.4](#)) treatment of all 16 subjects in one cohort in this trial is not considered to be an undue risk for enrolled subjects. However, treatment in cohorts for logistical reasons is possible. In this case, the cohorts should be of about the same size, e.g. two cohorts of 8 subjects, and be treated not too wide apart in terms of time for better comparability and reducing any possible factors influencing the readout.

An overview of all relevant trial activities is provided in the [Flow Chart](#). For visit schedule and details of trial procedures at selected visits, refer to [Sections 6.1](#) and [6.2](#), respectively.

#### 3.2 DISCUSSION OF TRIAL DESIGN, INCLUDING THE CHOICE OF CONTROL GROUP

##### Open-label design

This trial is conducted open-label. Blinding is not possible because the treatments are distinguishable. The open-label treatment is not expected to bias results, since the study endpoints are derived from measurement of plasma concentrations of the analytes provided by a bioanalytical laboratory which is blinded to treatment allocation.

##### Fixed sequence design

A fixed sequence design was selected due to the long half-life of both, memantine and BI 425809. The fixed-sequence design enables intra-individual comparisons and is not expected to lead to systematic errors in the estimation of the treatment effects, because the trial duration is short enough so that nonspecific time-effects are not expected.

Dosing durations are long enough to achieve steady-state drug exposures of both drugs reliably and to exclude any transient effects.

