Duration of treatment	
Period 1 = Visit 2: Treatment R1 (Reference 1 = BI 425809 alone)
 
Trial product 1: Days 1-10: multiple doses of 25 mg BI 425809 q.d.
 
Period 1 and 2 will be separated by a wash-out phase of at least 7 days between last treatment administration in Period 1 and first treatment administration in Period 2.
 
Period 2 = Visit 3: Up-Titration to R2 followed by Treatment R2 (Reference 2 = Memantine alone)
 
Trial product 2: Up-titration regimen to Treatment R2, i.e.
 
Days 1-7: multiple doses of 5 mg memantine q.d.
 
Days 8-14: multiple doses of 10 mg memantine q.d.
 
Days 15-21: multiple doses of 15 mg memantine q.d.
 
Days 22-28: multiple doses of 20 mg memantine q.d.
 
Trial product 2: Treatment R2, i.e.
 
Days 29-35: multiple doses of 20 mg memantine q.d
 
Period 3 = Visit 4: Treatment T (Test = BI 425809 + Memantine)
 
Trial product 1: Days 1-10 multiple doses of 25 mg BI 425809 q.d.
 
Trial product 2: Days 1-10 multiple doses of 20 mg memantine q.d.
 
Period 3 follow directly of period 2, i.e. the last day of period 2, is the calendar day before the first day of period 3.

Statistical methods	
The effects of BI 425809 on the pharmacokinetics of memantine (T to R1) and the effects of memantine on the pharmacokinetics of BI 425809 (T to R2) will be evaluated based on the ratio (test to reference treatment) of the point estimates of the geometric means (gMeans) for the primary and secondary PK endpoints. Additionally, their two-sided 90% confidence intervals (CIs) will be provided. This method corresponds to the two one-sided t-test procedure, each at a 5% significance level. Since the main focus is on estimation and not testing, a formal hypothesis test and associated acceptance range is not specified. The statistical model will be an analysis of variance (ANOVA) on the logarithmic scale including effects for 'subject' and 'treatment'. CIs will be calculated based on the residual error from the ANOVA.
 
Descriptive statistics will be calculated for all endpoints.

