#### 1.2.2.3 Clinical pharmacokinetics

After oral administration in humans, memantine is completely absorbed with an absolute bioavailability of approximately 100%. There is no indication that food influences the absorption of memantine.  $T_{max}$  is between 3 and 8 hours and memantine has demonstrated linear pharmacokinetics in the dose range of 10 to 40 mg in healthy volunteers [[R18-3740](#), [R18-3739](#)].

Daily doses of 20 mg lead to steady-state plasma concentrations of memantine ranging from 70 to 150 ng/ml (0.5 - 1  $\mu$ mol/L) with large interindividual variations. When daily doses of 5 to 30 mg were administered, a mean cerebrospinal fluid (CSF)/serum ratio of 0.52 was calculated. The volume of distribution is around 10 l/kg. About 45% of memantine is bound to plasma-proteins.

In humans, about 80% of the circulating memantine-related material is present as the parent compound. Main human metabolites are N-3,5-dimethyl-gludantan, the isomeric mixture of 4- and 6-hydroxy-memantine, and 1-nitroso-3,5-dimethyl-adamantane. None of these metabolites exhibit NMDA-antagonistic activity. No cytochrome P450-catalysed metabolism has been detected *in vitro* and memantine did not inhibit CYP1A2, 2A6, 2C9, 2D6, 2E1, 3A, Flavin-containing monooxygenase, epoxide hydrolase or sulphation *in vitro*. [[R18-3740](#), [R18-3739](#)]

Unchanged memantine is mainly excreted renally with a terminal  $t_{1/2}$  of 60 to 100 hours. Tubular secretion as well as tubular reabsorption are involved in its renal elimination. In vitro data suggest a potential role of MATE1 and OCT2 for renal secretion of memantine [[R17-3276](#), [R15-0935](#)] and also indicate that both, MATE1 and to an even higher extent OCT2, are inhibited by memantine, albeit with reported IC50 values that exceed unbound plasma concentrations expected during therapy [[R17-3276](#)]. The renal elimination rate of memantine under alkaline urine conditions may be reduced by a factor of up to 7 to 9. Alkalisation of urine may result from drastic changes in diet, e.g. from a carnivore to a vegetarian diet. Therefore, concomitant use of drugs that have an alkalinizing effect on the urinary pH, e.g. massive ingestion of alkalinising gastric buffers, or that compete at / inhibit the transporters of the renal cation transporter system (OCT2, MATE1) may theoretically lead to

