19. A marked baseline prolongation of QT/QTc interval (such as QTc intervals that are repeatedly greater than 450 ms in males or repeatedly greater than 470 ms in females) or any other relevant ECG finding at screening
20. A history of additional risk factors for *Torsade de Pointes* (such as heart failure, hypokalaemia, or family history of Long QT Syndrome)
21. Subject is assessed as unsuitable for inclusion by the investigator, for instance, because the subject is not considered able to understand and comply with study requirements, or has a condition that would not allow safe participation in the study

Female subjects will not be allowed to participate, if any of the following apply:

22. Positive pregnancy test, pregnancy, or plans to become pregnant within 30 days after study completion
23. Lactation

In addition, the following trial-specific exclusion criteria apply:

24. Any lifetime history of suicidal behaviour (i.e. actual attempt, interrupted attempt, aborted attempt, or preparatory acts or behaviour)
25. Any suicidal ideation of type 2 to 5 on the C-SSRS in the past 12 months (i.e. active suicidal thought without method, intent or plan; active suicidal thought with method but without intent or plan; active suicidal thought with method and

Proprietary confidential information © 2019 Boehringer Ingelheim International GmbH or one or more of its affiliated companies

intent but without specific plan; or active suicidal thought with method, intent and plan)

26. eGFR (CKD-EPI equation) < 80ml/min at screening
27. Liver tests (ALT, AST, GGT, AP), total bilirubin and creatinine outside the normal range at the screening examination
28. History of relevant liver diseases such as disturbance of liver function, jaundice, drug induced liver injury, Dubin-Johnson syndrome, Rotor syndrome, or liver tumors
29. Any presence or history of a condition linked with significantly elevated urine pH, including but not limited to renal tubular acidosis (RTA), severe infections of the urinary tract with Proteus bacteria.
30. Concomitant use of hormonal replacement therapy or hormonal contraceptives
31. Vegetarian diet or the purpose to switch from carnivore to vegetarian diet is not allowed during this trial due to potential urine alkalization.
32. History of macular degeneration or any abnormal finding in visual tests (Amsler grid test, colour discrimination test) at screening

For study restrictions, refer to [Section 4.2.2](#).

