### 7.2 NULL AND ALTERNATIVE HYPOTHESES

The relative bioavailability of BI 425809 administered alone compared with co-administration with memantine and the relative bioavailability of memantine administered alone compared with co-administration with BI 425809 will be estimated by the ratios of the geometric means (test/reference), and their corresponding 2-sided 90% confidence intervals (CIs) will be provided. This method corresponds to the two one-sided t-test procedure, each at the 5% significance level. Since the main focus is on estimation and not testing, a formal hypothesis test and associated acceptance range is not specified.

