### 7.3.1 Primary endpoint analyses

#### Primary analyses

The statistical model used for the analysis of the primary endpoints will be an analysis of variance (ANOVA) model on the logarithmic scale. That is, the PK endpoints will be log-transformed (natural logarithm) prior to fitting the ANOVA model. The model used will include effects accounting for the following sources of variation: subjects and treatment. The effect 'subjects' will be considered as random, whereas the effect 'treatment' will be considered as fixed. The model is described by the following equation:

$$y_{km} = \mu + s_m + \tau_k + e_{km}, \text{ where}$$

$y_{km}$  = logarithm of response measured on subject m receiving treatment k,

$\mu$  = the overall mean,

$s_m$  = the effect associated with the mth subject, m = 1, 2, ..., n,

$\tau_k$  = the kth treatment effect, k = 1, 2,

$e_{km}$  = the random error associated with the mth subject in who received treatment k.

where  $s_m \sim N(0, \sigma_B^2)$  i.i.d.,  $e_{km} \sim N(0, \sigma_W^2)$  i.i.d. and  $s_m, e_{km}$  are independent random variables.

Point estimates for the ratios of the geometric means (test/reference) for the primary endpoints (see [Section 2.1](#)) and their two-sided 90% confidence intervals (CIs) will be provided.

For each endpoint, the difference between the expected means for log(T)-log(R) will be estimated by the difference in the corresponding adjusted means (Least Squares Means). Additionally their two-sided 90% confidence intervals will be calculated based on the residual error from the ANOVA and quantiles from the t-distribution. These quantities will then be back-transformed to the original scale to provide the point estimate and 90% CIs for each endpoint.

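### Does residual memantine accumulation between the R2 and T profiles bias T/R2 enough to need a change?

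*Protocol*

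**What the plan says.** The synopsis gives memantine at 5, 10 and 15 mg for seven days each, and then "Days 22-28: multiple doses of 20 mg memantine q.d". Treatment R2 adds seven more days at 20 mg (Days 29 to 35). There is no break before the combination: "Period 3 follow directly of period 2". Period 3 has ten days of both drugs. CTP 4.2.2.2 sets the memantine steady-state profile days at Day 35 of Visit 3 (R2) and Day 10 of Visit 4 (T).

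CTP 1.2.2.3 gives memantine linear kinetics from 10 to 40 mg and a terminal half-life "of 60 to 100 hours. Tubular secretion as well as tubular reabsorption" being involved in its renal elimination.

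CTP 3.2 defends the fixed sequence on two grounds. It expects no systematic error "because the trial duration is short enough so that nonspecific time-effects are not expected", and it adds: "Dosing durations are long enough to achieve steady-state drug exposures of both drugs reliably and to exclude any transient effects".

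On analysis, CTP 7.3.1 states: "The model used will include effects accounting for the following sources of variation: subjects and treatment". CTP 7.2 states: "Since the main focus is on estimation and not testing, a formal hypothesis test and associated acceptance range is not specified". Table 7.7: 1 gives a memantine precision of 1.063 (94.03 to 106.34%) for 16 subjects at a gCV of 7.7%.

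**The concern.** The word any in the CTP 3.2 clause is absolute, and a half-life of up to 100 hours means that accumulation is not quite finished after 14 doses. Every subject has the R2 profile first and the T profile ten days later on continued memantine. Any remaining rise therefore coincides exactly with the switch from R2 to T. With only subject and treatment in the model, the rise is counted in T/R2 as if BI 425809 had caused it. The fixed-effects repeat of the model cannot separate the two either.

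The memantine comparison is also planned to be tight, so even a small shift is visible against the interval. Someone who checks whether the 90% interval excludes 1 could read a slight kinetic artefact as a slight increase due to BI 425809, or could miss a slight decrease.

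**Working it through.** **1. Reproduce the planned precision.** Inputs from CTP 7.7: gCV 0.077, n = 16, two-sided 90% interval, 95% assurance.

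- Within-subject SD on the log scale: s = sqrt(ln(1 + 0.077²)) = 0.0769
- SE of the log ratio: 0.0769 × sqrt(2/16) = 0.0272
- t quantile (0.95, 15 df) = 1.753; assurance factor sqrt(24.996/15) = 1.291
- Precision = exp(1.753 × 0.0272 × 1.291) = 1.0634, and 1/1.0634 = 0.9403

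This matches the table row, and the same formula reproduces all 16 rows. Without the assurance factor the half-width is 1.753 × 0.0272 = 0.0477, or about 4.9%.

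**2. Fraction of steady state.** Assume linear one-compartment accumulation at the stated half-life (h hours), with linearity extended to the 5 mg step. Let r = 2^(−24/h). For doses rising by 5 mg every seven days to 20 mg, the fraction of 20 mg steady state at dose n is

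F(n) = 1 − [r^n + r^(n−7) + r^(n−14) + r^(n−21)] / 4

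R2 is n = 35 and T is n = 45. At 80 h:

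- F(35) = 1 − (0.0007 + 0.0030 + 0.0127 + 0.0544)/4 = 0.9823
- F(45) = 1 − (0.0001 + 0.0004 + 0.0016 + 0.0068)/4 = 0.9978
- T/R2 with no interaction = 0.9978/0.9823 = 1.0158

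**3. Range, and what it does to the interval.** The share of precision is ln(T/R2) / ln(1.0634), with ln(1.0634) = 0.0615. Coverage and the last row come from the non-central t distribution with 15 df and non-centrality ln(T/R2)/0.0272.

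| Half-life | 60 h | 80 h | 100 h |
|---|---|---|---|
| R2, % of steady state | 99.4 | 98.2 | 96.5 |
| T, % of steady state | 99.96 | 99.8 | 99.3 |
| T/R2, no interaction | 1.0057 | 1.0158 | 1.0294 |
| Share of planned precision (log scale) | 9% | 25% | 47% |
| Coverage of 1 by the 90% interval | 89% | 85% | 73% |
| Interval wholly above 1 (nominal 5%) | 7% | 14% | 27% |

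Adding absorption with the stated tmax of 3 to 8 h raises the 100 h figure only to about 1.030, for AUC and Cmax alike. The titration doses must be credited; ignoring them would wrongly give 2.0 to 8.7%.

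**4. A central value.** Averaging over 60 to 100 h gives +1.4 to +1.6%, depending on the shape assumed for the half-life distribution. If the effective half-life were shorter (46 to 77 h, an assumption), the shift would be 0.2 to 1.4%. The documents do not settle which applies.

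**5. BI 425809.** R1 and T are both profiled at the tenth dose, so a shortfall from incomplete accumulation is the same in both and cancels.

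**6. What a reading band would do.** One response would be to read the memantine interval against 1.00 to 1.03. With no interaction, an interval wholly above 1.03 arises in 0.7% of trials at 60 h and 1.6% at 80 h, well under the nominal 5%. For a true +5%, it arises in 22% at 60 h and 34% at 80 h. A drift-free trial read against 1.00 would show an interval wholly above 1 in 53%. The band over-corrects, because it is set at the 100 h end of the range.

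**The case for a change.** The best case for a change is that the bias is predictable, goes one way, follows from the protocol's own half-life and falls wholly into an estimate that the plan calls its main focus. At 80 h it is about a third of the expected half-width (0.0156/0.0477 = 0.33). It also works in the other direction: a true 5% decrease would give an interval wholly below 1 in 48, 35 or 19% of trials at 60, 80 or 100 h, against 56% without drift. A few sentences of disclosure would cost almost nothing.

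The arithmetic stands, and so does the point that the clause, read literally, claims a little too much. The harm does not carry the same weight:

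- The percentages for intervals above or below 1 are significance readings, and CTP 7.2 sets those aside.
- The upper end of the half-life range is less plausible here, because the protocol excludes "eGFR (CKD-EPI equation) < 80ml/min at screening", vegetarian diets and conditions that raise urine pH. This is an inference; the documents give no half-life by renal function.
- The wording is open. The first half of the sentence already covers reaching steady state, so transient effects may mean something else, such as the onset of an interaction.
- The Flow Chart schedules memantine pre-dose samples on Days 33 to 35 of Visit 3 and Days 1, 5, 6, 9 and 10 of Visit 4. Whoever discusses a ratio close to 1 can look at attainment directly. Some further-PK sections are not in the public text, so a missing check cannot be claimed.

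**Conclusion.** No change is needed. The drift is real but small: about 0.6% at 60 h, 1.6% at 80 h and up to 3.0% at 100 h, under linear one-compartment accumulation with the stated terminal half-life taken as the accumulation half-life. At 96.5 to 99.4% of steady state, R2 is an acceptable steady-state reference. Within the stated half-life range the shift stays below half the planned precision on the log scale. No test or acceptance range depends on it, and an interaction of any practical size would still be seen.

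The trade-off is fair. The sequence is fixed because both half-lives are long, and ten more doses of memantine between profiles are the price of studying the combination without a second titration. Softening the clause in CTP 3.2 would be harmless, but it would change no analysis, result or conclusion. A reading band up to 1.03 would be worse than the problem. A memantine ratio a percent or two above 1 should be discussed with the half-life and the scheduled pre-dose values in view, which a pharmacokineticist would do anyway.

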#### 3.3 SELECTION OF TRIAL POPULATION

It is planned that 16 healthy male or female subjects will enter the study. They will be recruited from the volunteer's pool of the trial site.

A log of all subjects enrolled into the trial (i.e. who have signed informed consent) will be maintained in the ISF irrespective of whether they have been treated with investigational drug or not.

### 3.3.1 Main diagnosis for trial entry

The study will be performed in healthy subjects.

### 3.3.2 Inclusion criteria

Subjects will only be included in the trial if they meet the following criteria:

1. Healthy male or female subjects according to the assessment of the investigator, as based on a complete medical history including a physical examination, vital signs (BP, PR), 12-lead ECG, and clinical laboratory tests
2. Age of 18 to 50 years (inclusive)
3. BMI of 18.5 to 29.9 kg/m^2 (inclusive)
4. Signed and dated written informed consent prior to admission to the study, in accordance with GCP and local legislation
5. Male subjects, or female subjects who meet any of the following criteria from the first administration of trial medication until 30 days after trial completion:
  - Use of adequate contraception that does not contain hormones, i.e. non-hormonal intrauterine device *plus* condom
  - Sexually abstinent
  - A vasectomised sexual partner (vasectomy at least 1 year prior to enrolment)
  - Surgically sterilised (including hysterectomy)
  - Postmenopausal, defined as at least 1 year of spontaneous amenorrhea (in questionable cases a blood sample with levels of FSH above 40 U/L and estradiol below 30 ng/L is confirmatory)

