4. End of trial examination includes physical examination including neurological assessment, vital signs, visual tests, C-SSRS assessment, ECG, safety laboratory, recording of AEs and concomitant therapies.
5. Only urine drug screening and alcohol breath test as well as pregnancy test in women will be done at this time
6. AEs and concomitant therapies will be recorded throughout the trial, but will be specifically asked for at the times indicated in the [Flow Chart](#) above.
7. There will be no further wash-out period between visit 3 and 4, i.e. Day 1 of Visit 4 the following calendar day of Day 35 visit 3
8. The sample is to be taken within 10 min prior to next dosing
9. During the up-titration phase to steady state vital signs, ECG and AE/CT questioning is performed on each day prior to memantine medication
10. During the up-titration phase to steady state safety lab is taken at the last day of each memantine dose level
11. Only on day 22 and 33
12. Neurological assessment for details refer to [Section 5.2.1](#)
13. A blank urine sample (x) is to be obtained prior to administration of trial medication. Other urine samples are to be collected over the stated post-dose intervals as indicated above. For technical reasons the planned stop time of the urine sample obtained starting visit 3, 828:00, will be 840:00.
14. Only on day 28
15. The column “planned time” only includes start time of the first day of the respective interval of days
16. To be done on the first day of each dose level
17. Visual tests, for details refer to [Section 5.2.3](#)
18. Period 1 and 2 will be separated by a wash-out phase of at least 7 days between last treatment administration in Period 1 and first treatment administration in Period 2

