### 3.3.3 Exclusion criteria

Subjects will not be allowed to participate, if any of the following general criteria apply:

1. Any finding in the medical examination (including BP, PR or ECG) deviating from normal and assessed as clinically relevant by the investigator
2. Repeated measurement of systolic blood pressure outside the range of 90 to 140 mmHg, diastolic blood pressure outside the range of 50 to 90 mmHg, or pulse rate outside the range of 50 to 90 bpm
3. Any laboratory value outside the reference range that the investigator considers to be of clinical relevance
4. Any evidence of a concomitant disease assessed as clinically relevant by the investigator
5. Gastrointestinal, hepatic, renal, respiratory, cardiovascular, metabolic, immunological or hormonal disorders
6. Cholecystectomy or other surgery of the gastrointestinal tract that could interfere with the pharmacokinetics of the trial medication (except appendectomy or simple hernia repair)

Proprietary confidential information © 2019 Boehringer Ingelheim International GmbH or one or more of its affiliated companies

7. Diseases of the central nervous system (including but not limited to any kind of seizures or stroke), and other relevant neurological or psychiatric disorders
8. History of relevant orthostatic hypotension, fainting spells, or blackouts
9. Chronic or relevant acute infections
10. History of relevant allergy or hypersensitivity (including allergy to the trial medication or its excipients)
11. Use of drugs within 30 days of planned administration of trial medication that might reasonably influence the results of the trial (including drugs that cause QT/QTc interval prolongation)
12. Intake of an investigational drug in another clinical trial within 60 days of planned administration of investigational drug in the current trial, or concurrent participation in another clinical trial in which investigational drug is administered
13. Smoker
14. Alcohol abuse (consumption of more than 12 g per day for females and 24 g per day for males)
15. Drug abuse or positive drug screening
16. Blood donation of more than 100 mL within 30 days of planned administration of trial medication or intended blood donation during the trial
17. Intention to perform excessive physical activities within one week prior to the administration of trial medication or during the trial
18. Inability to comply with the dietary regimen of the trial site

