### **4.2.2.2    Restrictions on diet and life style**

While admitted to the trial site, the subjects will be instructed not to consume any foods or drinks other than those provided by the staff. Standardised meals will be served at standard times if not indicated otherwise in the [Flow Chart](#).

On all dosing days, the trial medication will be administered after an overnight fast of at least 10 h prior. Fluid intake is not allowed from 1 h pre-dose until drug administration.

On PK profile days (Day 1 and 10, Visit 2; Day 1 and 35, Visit 3 and Day 10, Visit 4) subjects will remain fasted until 4 hours after administration. Their fluid intake is restricted to the water administered with the drug and an additional 240 mL of water served at 2 h and 4 h post-dose (mandatory for all subjects) from 1 hour before drug intake until 4 hours post dose. From lunch until 24 h post-dose, subjects are advised that total fluid intake should be in the range of 2000 - 3000 mL.

On all other dosing days subjects have to remain fasted for 1 h after drug administration.

Proprietary confidential information © 2019 Boehringer Ingelheim International GmbH or one or more of its affiliated companies

Alcoholic beverages, grapefruits, Seville oranges (sour or bitter oranges) and their juices, and dietary supplements and products including St. John's wort (*Hypericum perforatum*) are not permitted starting 7 days before the first administration of trial medication until after the last PK sample of each study period is collected.

Methylxanthine-containing drinks or foods (such as coffee, tea, cola, energy drinks, and chocolate) are not allowed from 24 h before until 24 h after each administration of trial medication.

Excessive physical activity (such as competitive sport) should be avoided starting 7 days before the first administration of trial medication until the end of trial examination.

Direct exposure to the sun or exposure to solarium radiation should be avoided during the entire study.

A switch from carnivore to vegetarian diet is not allowed during this trial due to potential urine alkalinisation.

If female subjects of child-bearing potential are included in the trial, adequate contraception is to be maintained throughout the course of the trial (see [Section 3.3.2](#) for the definition of adequate measures). Hormonal contraception is not allowed.

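### The contraception requirement starts only at the first dose, so a conception just before Day -1 is neither ruled out by eligibility nor reliably caught by testing

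*Protocol*

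**What the plan says.** Inclusion criterion 5 (Protocol Section 3.3.2) admits men, or "female subjects who meet any of the following criteria from the first administration of trial medication until 30 days after trial completion". The listed options are non-hormonal intrauterine device plus condom, abstinence, a partner vasectomised at least 1 year before enrolment, surgical sterility, and at least 1 year of menopause.

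Four other parts of the protocol bear on the point:

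- **Section 4.2.2.2** states that, for women of child-bearing potential, "adequate contraception is to be maintained throughout the course of the trial". It refers to Section 3.3.2 for what counts as adequate and gives no start date.
- **Section 3.3.3, exclusion 22** bars "Positive pregnancy test, pregnancy, or plans to become pregnant within 30 days after study completion". **Exclusion 30** bars "Concomitant use of hormonal replacement therapy or hormonal contraceptives".
- **Table 5.2.5: 1** specifies a urine beta-HCG test at screening, and screening may fall anywhere from Day -21 to Day -1.
- **Flow Chart, footnote 5**, attached to the Day -1 admission and to later admissions, reads "Only urine drug screening and alcohol breath test as well as pregnancy test in women will be done at this time".

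**The concern.** The rule protects the period after the trial but not the days before dosing. Sterilised and postmenopausal women, and those with a vasectomised partner, are covered because their status predates dosing by definition. Abstinence carries no such condition: a woman abstinent only from Day 1 meets the criterion as written. An intrauterine device would often be in place earlier, but nothing requires it.

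Exclusion 30 sharpens this. A woman who stops a hormonal method in order to enter has no obligation under criterion 5 to replace it until Day 1.

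Exclusion 22 cannot exclude a pregnancy that does not yet test positive. Following the protocol exactly, the site could therefore dose a woman in very early pregnancy. Section 1.4 states that participants gain no therapeutic benefit, so nothing offsets that exposure. The stake is subject safety only.

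**Working it through.** The protocol gives no figure of its own to reproduce. The arithmetic uses Flow Chart times, counted from the first BI 425809 dose at 0 h.

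**Inputs from the documents**

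- Day -1 pregnancy test: -14 h.
- Next test, Visit 2 Day 9 admission: 202 h.
- BI 425809 25 mg at 0, 24, ..., 216 h (10 doses).
- Periods 1 and 2 are separated by a "wash-out phase of at least 7 days between last treatment administration in Period 1" and the first dose of Period 2. Visit 3 Day 1 dosing is therefore no earlier than 216 + 168 = 384 h, with its admission test 2 h before, at 382 h.

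**Intervals and doses**

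- Day -1 to Day 9 test: 202 + 14 = 216 h = 9.0 days. Doses at 0 to 192 h: 9 × 25 = 225 mg.
- Day -1 to Visit 3 Day 1 test: 382 + 14 = 396 h = 16.5 days at the least. Doses: 10 × 25 = 250 mg.

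**Assumption not in the documents.** Urine beta-HCG turns positive L days after conception, with L between 7 and 14. The protocol states neither assay sensitivity nor a detection lag.

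A conception t days before the Day -1 test is missed on Day -1 if t < L. It is still missed on Day 9 if t + 9.0 < L.

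| L (days) | Missed on Day -1 | Still negative on Day 9 |
|---|---|---|
| 7 | last 7 days | none |
| 10 | last 10 days | last 1 day |
| 14 | last 14 days | last 5 days |

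Because 16.5 exceeds 14, every case in this range can be detected at Visit 3 Day 1. The screening test does not narrow the window, since it takes place no later than Day -1. Being in-house from the evening of Day -1 (Section 6.2.2) prevents conception after admission, but the uncovered days come before it.

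**If Section 4.2.2.2 is read as starting at consent.** The Day -1 test is at 18:00. Seven days earlier is Day -8 at 18:00, and fourteen days earlier is Day -15 at 18:00. Consent on Days -7 to -1 (7 of the 21 permitted screening days) leaves at least part of a 7-day window open. Consent on Days -14 to -1 (14 of 21) does the same for a 14-day window. These are counts of calendar days, not proportions of women.

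**Lead-in needed.** To cover a 14-day window before the Day -1 test: 14 × 24 + 14 = 350 h = 14.6 days before the first dose. A 30-day lead-in reaches 720 - 14 = 706 h = 29.4 days before that test.

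**The case against.** The strongest reply is that Section 4.2.2.2 already binds women earlier. Section 3.3 equates enrolment with signed consent, and Section 8.6 dates the start of the trial from the first enrolment, so the course of the trial could fairly be read as beginning at consent. That reading narrows the gap. It does not close it, because consent may come on Day -1 and no minimum interval is guaranteed.

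Second, the exposed group is small: some of the women among 16 subjects, excluding those whose status predates dosing and those planning pregnancy. Testing is repeated, Section 3.3.4 requires dosing to stop at once if pregnancy becomes known, and across the assumed lag range the Visit 3 Day 1 test comes before any memantine is given. Section 1.2.1.2 reports that embryo-foetal studies support dosing women of child-bearing potential, with no fetotoxicity or teratogenicity for the two major metabolites. All of this stands and limits the harm. However, testing and stopping act only after exposure, and the toxicology support is itself conditional on a medically acceptable method of contraception.

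Third, 30 days is more than the assumed lag requires, and it reaches back before the earliest screening day, so part of it would rest on self-report. That is true: about 15 days would cover the range. But self-reported 30-day look-backs are already accepted here, in exclusion 11 ("Use of drugs within 30 days of planned administration of trial medication") and exclusion 16 ("Blood donation of more than 100 mL within 30 days of planned administration of trial medication"). The longer interval also gives margin against an unstated assay lag.

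**Conclusion.** The concern holds. Criterion 5 has no lead-in, and no other provision guarantees one. Under the assumed lag, the blind window is the 7 to 14 days before the Day -1 test, and the possible exposure is 9 to 10 doses of BI 425809 (225 to 250 mg). The reading of the text is firm, but the size of the window depends wholly on the assumed lag. The documents do not allow an expected number of cases to be calculated; the probability is low. The primary pharmacokinetic comparisons and N = 16 are unaffected. This is an inexpensive safety correction that should be made, not a flaw that threatens the trial.

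**What to change.** In criterion 5, move the start of the requirement from the first administration of trial medication to at least 30 days before it, and keep the existing 30-day tail. State the same start point in Section 4.2.2.2 so that the two sections agree.

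The cost is one line in each section, made by amendment. A few women may be ineligible or have to start later, for example those changing from a hormonal method. No visits, tests or subjects are added.
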